4.12.1 Pharmacokinetic Concentrations

Concentration Listings:

Pharmacokinetic concentration data for ALXN1910, will be listed by cohort, dose, day, route of administration (SC/IV), ethnicity category (Japanese/Non-Japanese), sex, age, weight, and participant for the SAF. Concentration listings will include nominal PK sampling time relative to dose administration or to start of infusion, actual sampling times relative to dose administration or actual sampling time relative to start of infusion, infusion duration, deviation from nominal time, and percent deviation from nominal time, and concentrations. Serum concentrations below the lower limit of quantification (LLOQ) will be presented as below the limit of quantification (BLQ) in the listings and the LLOQ value presented as a footnote. Missing PK samples will be reported as no sample (NS) or not reportable (NR) as appropriate and considered excluded from PK analysis.

Concentration Summary Tables:

Source data as reported from the laboratory will be used for calculation of concentration summary statistics. Tabular summaries for concentration-time data will report N (The number of Participants included in the pharmacokinetic analysis set for each treatment), n (number of participants with non-missing values), and n(BLQ) (the number of participants with BLQ samples).

Concentration for ALXN1910 will be summarized by cohort, dose and route of administration (SC/IV), and nominal timepoint for the PK set. The following descriptive statistics will be presented for Serum concentrations obtained at each nominal time point: N, n, n(BLQ), arithmetic mean, SD, coefficient of variation (CV%), geometric mean, geometric CV% (calculated as: $gCV\% = SQRT(e^{s^2}-1)*100$; where s is the SD of the log-transformed values), median, minimum, and maximum values.

Statistical Analysis Plan

For summary tables, all BLQs will be considered zero, and the number of BLQs at each scheduled time point will be reported. Summary statistics will not be calculated if non-BLQ concentrations at a scheduled time point is <3 and will be reported as NC (not calculated).

The rules followed for calculation and presentation of concentration data with regards to the number of decimal places/significant digits for the listings of participant level concentrations and summary tables of concentration are as follows:

Concentration Listings and Tables	Rounding
Individual concentrations	n s f. as supplied by bioanalytical laboratory

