	bonsor specific requirements) from summary tables and statistical analysis of PK neters. All the derived parameters (i.e. $t^{1/2}$, AUC _∞ , CL/F and Vd/F (SC) or CL V_d (IV)) may also be flagged in listings and excluded from statistical analysis of arameters. %AUC _{ex} may also be flagged in listings, but not excluded. The reason agging/exclusion will be listed/footnoted in parameter listings.						
	6. The t ¹ / ₂ will be calculated as follows: $t^{1}/_{2} = \ln 2/\lambda z = 0.693/\lambda z$						
	7. Data points may be dropped from the linear regression if the PK Scientist considers the reported values to be anomalous. Any data points so designated should remain in the listings with a footnote and be identified in the study report with a rationale for exclusion.						
CL or CL/F	Following IV or SC administration, systemic clearance of parent drug will be calculated from: $CL \text{ or } CL/F = \frac{Dose}{AUC_{\infty}}$						
	CL for IV cohorts and CL/F for SC cohorts						
V _d or V _d /F	Volume of distribution at terminal phase following either intravascular or subcutaneous dosing may be calculated from:						
	V_d or $V_d/F = \frac{Dose}{\lambda_z \times AUC_{\infty}} = CL / \lambda_z$ or (CL/F)/ λ_z						
	Vd for IV cohorts and Vd/F for SC cohorts						
DNC_{max} , $DNAUC_t$ and $DNAUC_{\infty}$	Parameter value divided by dose						

PK Parameters Listings:

PK parameters will be listed by participant, cohort, dose, administration route and Japanese/non-Japanese for the SAF. PK parameters that will be flagged and/or excluded from summary tables and statistical analyses of PK parameters will be flagged and footnoted with the reason for flagging/exclusion.

PK Parameter Summary Tables:

Biostatistics group will consider the derived PK parameters as source data and will use this data without rounding for calculation of PK parameters summary statistics tables.

PK parameters will be summarized by cohort, dose and route of administration (SC /IV), as appropriate for the PK set. Tabular summaries for PK parameters will report N (The number of Participants included in the pharmacokinetic analysis set for each treatment) and n (number of subjects with a specific parameter).

Descriptive statistics for calculated PK parameters will include N, n, arithmetic mean, SD, CV%, geometric mean, gCV%, median, minimum, and maximum values. For t_{max} , only N, n, median,

Statistical Analysis Plan

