4.12.4 Statistical Analysis of Pharmacokinetic Parameters

* Assessment of Absolute Bioavailability

The absolute bioavailability (F) for the ALXN1910 SC cohorts will be defined by the ratio of the geometric means for the area under the serum concentration-time curve from time 0 (dosing) to infinity parameter for the ALXN1910 SC cohort (cohort 2, 15 mg) over the ALXN1910 IV cohort (cohort 3, 15 mg).

A mixed effect model will be performed to the ln-transformed AUC_{∞} and the independent variables will include fixed effects for treatment and participant as a random effect. Geometric least-squares means for each treatment (SC or IV), point estimates and associated 95% CIs for the ratios for AUC_{∞} will be produced in tabular format. This will be anti-log transformed to obtain the point estimates and the 95% CI for the geometric mean ratio on the original scale. Estimates of between -participant variability (%CV) will also be provided.

SAS code for this analysis is mentioned in Section 6.5.

* Assessment of Dose Proportionality

Power model using linear regression method:

Dose proportionality will be assessed for sc cohorts, Non-Japanese only, for C_{max} and AUC (AUC_t, AUC_{∞}) using the PKAS who received single dose of ALXN1910 SC (Cohort 2, 5, and 6). PK parameters will be used to perform a LS linear regression analysis, using the formula ln_PK parameter =A× ln_dose + B, where 'ln PK Parameter' represents the natural log transformed C_{max} and AUC parameters and 'ln_dose' represents the natural log-transformed dose, A is the slope of the regression line and B is the intercept of the lines. The estimate obtained for A is a measure of dose proportionality.

Alexion Pharmaceuticals, Inc.	
ALXN1910-HV-101	Statistical Analysis Plan

An estimate of the slope and intercept of the regression line and corresponding 95% CI will be obtained for each PK parameter (C_{max} , AUC_t, and AUC_{∞}).

SAS code for this analysis is mentioned in Section 6.5.

Dose-proportionality based on the power model will be accepted ("not rejected", in terms of statistical inference) if the 95% CIs of the slope does not include 0 for each PK parameter.

Figure for Dose-Proportionality with 95% CI will be presented.

✤ Assessment of Ethnicity Comparison

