The PK parameters for ALXN1910 will be evaluated for Japanese and non-Japanese participants (Cohort 2 versus Cohort 4) on active treatment, using an analysis of variance statistical model with cohort as the fixed effects on the natural logarithms of the data. In addition, the Japanese versus non-Japanese cohorts will be evaluated using descriptive statistics; for each cohort, the geometric means and the associated 95% CIs of difference of PK parameters will be reported.

PK parameters will be separately analyzed using a mixed effects model. The dependent variable will be the log-transformed PK parameters of interest (AUC $_{\infty}$, AUC_t and C_{max}) and the independent variables will include a fixed effect for ethnicity (Japanese vs non-Japanese) and participant as a random effect.

The estimated difference and CI obtained on the log scale will be exponentiated to provide an estimate of the Japanese to non-Japanese ratio and its associated 95% CI. Estimates of between -participant variability (%CV) will also be provided.

Plots of adjusted GMR of Japanese to non-Japanese together with 95% CIs will be produced.

SAS code for this analysis is mentioned in Section 6.5.

4.12.5 Pharmacodynamic Analysis, Concentration, and Parameter TFLs, and Statistical Analysis of Pharmacodynamic Parameters

Individual participant PPi versus time profiles values, both observed and change from baseline, will be calculated by Charles River Lab and Individual participant PLP, PL, PA versus time profiles values, both observed and change from baseline, will be calculated by PPD Laboratories respectively. Baseline observed, observed, change from baseline, and percent change from Baseline PPi, PLP, PL, PA versus time profiles values will be listed by treatment, sampling time and participant. Listings will include actual sampling times relative to dose administration, observed PPi, PLP, PL, PA versus time profiles value, change from baseline value, and percentage change from baseline. Baseline will be taken as the last measurement prior to dosing, see Section 6.1 Descriptive statistics (number, mean, SD, CV%, minimum, median, and maximum) will be presented by dose cohort, including pooled placebo, pooled active treatment across cohorts, pooled IV cohorts, pooled SC cohorts and overall for absolute, and percentage change from baseline PD assessment, time of minimum and time of maximum will only have minimum, maximum, and median time.

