6.5 Sample SAS Code for statistical analysis

Dose proportionality analysis

ODS OUTPUT parameterestimates=est FitStatistics=fit;

PROC REG DATA = PP ALPHA=0.05 PLOTS=ALL;

BY PARAMCD PARAM;

MODEL LNAVAL=LNDOS/CLB;

RUN;

where:

LNAVAL: natural log-transformed PK parameter

LNDOS: natural log-transformed dose level of ALXN1910

PARAM: PK parameter

SUBJECT: participant

ALXN1910-HV-101

Statistical Analysis Plan

Absolute Bioavailability analysis

ODS SELECT NOPRINT(NOWARN);

ODS OUTPUT CovParms= Cv1 lsmeans=lsm estimates=est Diffs=diff1;

PROC MIXED DATA=DATA1 NOITPRINT;

BY COMPOUND PPSPEC PARAMN PARAMCD PARAM;

CLASS SUBJID TRTA;

MODEL LN_PK = TRTA/DDFM=KR;

RANDOM SUBJID;

LSMEANS TRTA/PDIFF ALPHA=0.05 CL;

ESTIMATE "SC vs IV" TRTA 1 -1 /CL ALPHA=0.05;

RUN;

where:

COMPOUND: compound used in the study

PPSPEC : Specification (Serum)

PARAMN : numerical order of PK parameter

PARAMCD :short name of PK parameter

PARAM: PK parameter

LN_PK; natural log transformed value of PK parameter

SUBJID: Participant

TRTA: actual treatment

Ethnicity Comparison

Sample SAS Code:

ODS SELECT NOPRINT(NOWARN);
ODS OUTPUT CovParms= Cv1 lsmeans=lsm estimates=est Diffs=diff1;
PROC MIXED DATA=DATA1 NOITPRINT;
BY COMPOUND ANALYTE PPSPEC PARAMN PARAMCD PARAM;
CLASS SUBJID ETHNICITY;
MODEL LN_PK = ETHNICITY/DDFM=KR;
RANDOM INT SUBJID ;
LSMEANS ETHNICITY/PDIFF ALPHA=0.05 CL;
ESTIMATE "JAPANESE vs NON-JAPANESE" ETHNICITY 1 -1 /CL ALPHA=0.05;

RUN;

where:

Statistical Analysis Plan

COMPOUND: compound used in the study

ANALYTE : analyte of the drug (can be parent or metabolite)

PPSPEC : Specification (serum)

PARAMN : numerical order of PK parameter

PARAMCD :short name of PK parameter

PARAM: PK parameter

LN_PK; natural log transformed value of PK parameter

SUBJID: Participant

Approval Signatures

Document Name:	Statistical Analysis Plan 28 Mar 2023 ALXN1910-HV-101
Document Number:	VV-TMF-3755505
Parexel Version Number:	
System Version Number:	1.0

Document Approvals	PPD
Reason for signing: Approved	
Reason for signing: Approved

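### The bioavailability and Japanese/non-Japanese PK models fit a random participant effect to one value per participant, so the promised between-participant %CV is not identifiable

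*SAP*

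**What the plan says.** SAP 4.12.4 models ln AUC∞ for absolute bioavailability, 15 mg SC (Cohort 2) against 15 mg IV (Cohort 3): "the independent variables will include fixed effects for treatment and participant as a random effect". For the Japanese/non-Japanese comparison (Cohort 2 against Cohort 4) it models ln AUC∞, AUCt and Cmax: "the independent variables will include a fixed effect for ethnicity (Japanese vs non-Japanese) and participant as a random effect". Each part ends with the same promise: "Estimates of between -participant variability (%CV) will also be provided".

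The ethnicity part also gives, one paragraph earlier, a plain ANOVA of ln PK on cohort. That is the model in protocol 9.4.2.1, so one comparison carries two model descriptions.

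In SAP 6.5 both programs run by PK parameter with Kenward-Roger degrees of freedom. The bioavailability program has "RANDOM SUBJID" and the ethnicity program has "RANDOM INT SUBJID". Both save the covariance parameters ("ODS OUTPUT CovParms= Cv1 lsmeans=lsm estimates=est Diffs=diff1"), but no text selects a row or gives a formula for the %CV.

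The only CV formula in the SAP is the geometric CV in 4.12.1, "where s is the SD of the log-transformed values", and it belongs to the concentration tables. Section 4.12.2 adds cohort-level summaries of the PK parameters: "Descriptive statistics for calculated PK parameters will include N, n, arithmetic mean, SD, CV%, geometric mean, gCV" and further statistics.

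**The concern.** A random participant effect can be separated from residual error only if some participants contribute more than one value to the fit. Here none does. The model asks for two variances where the data inform one. The natural reading of a between-participant %CV is the participant row of the covariance table, which is the quantity the data cannot determine.

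The ethnicity program goes further. Its random intercept has no `SUBJECT=` option, so it is a single intercept common to everyone and is aliased with the fixed intercept.

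At stake are a reported %CV that depends on software handling rather than on data, and a fit whose variance information matrix is singular, on which the requested degrees-of-freedom method relies. A number of this kind could be printed beside the well-defined cohort gCV% and carried forward into later planning.

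**Working it through.** The plan states no figure on this point, so there is nothing to reproduce first.

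**Inputs from the documents**
- 8 participants per cohort at 3:1, so 6 on active; one dose each (SAP 3.1, Table 1).
- One set of PK parameters per participant after that dose (SAP 3.3.2). No crossover or repeat dosing is planned, and protocol exclusion criterion 14 bars participation in this study within the previous 90 days.
- Each fit is for one PK parameter (SAP 6.5), giving 6 + 6 = 12 rows from 12 different people.

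**Assumption.** Total ln-variance 0.09. The documents give no variability figure, so other values are shown below.

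**Step 1: covariance.** With one row per participant, V = s²_subj·I + s²_res·I = (s²_subj + s²_res)·I. Only the sum appears.

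**Step 2: likelihood and %CV by split.** The check used a deterministic 6 + 6 data set with pooled ln-variance exactly 0.09, and %CV = 100·sqrt(exp(s²_subj) - 1):

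| Participant share | s²_subj | REML log-likelihood | Participant-row %CV |
|---|---|---|---|
| 0% | 0 | -3.9414 | 0 |
| 25% | 0.0225 | -3.9414 | 15.1 |
| 50% | 0.0450 | -3.9414 | 21.5 |
| 75% | 0.0675 | -3.9414 | 26.4 |
| 99% | 0.0891 | -3.9414 | 30.5 |
| 100% | 0.0900 | -3.9414 | 30.7 |

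On a simulated 6 + 6 data set with pooled variance 0.0369, the log-likelihood was 9.7117 at every split and the participant-row %CV ran from 0 to 19.4%.

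For other assumed totals, the participant-row %CV ranges over 0-20% (14.1% at an even split) if the total CV is 20%, and over 0-50% (34.4% at an even split) if it is 50%.

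**Step 3: information.** For the total variance v on 10 df, the information is 10/(2v²) = 5/0.0081 = 617.3. Every entry of the 2 × 2 REML Hessian is -617.3, with eigenvalues -1234.6 and 0: rank 1 of 2. The shared intercept in the ethnicity code adds a zero row and column: rank 1 of 3. Giving that intercept a variance of 0.1 or 1 changes neither the log-likelihood nor the SE.

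**Step 4: what is not affected.** The SE of the ln ratio is sqrt(0.09 × (1/6 + 1/6)) = sqrt(0.03) = 0.1732 at every split. On 10 df the 95% CI is the ratio divided and multiplied by exp(2.228 × 0.1732) = 1.471. With the predicted AUC over 168 h from protocol Table 6 as placeholders:
- SC/IV: 136.0/225.1 = 0.604 (0.411 to 0.889).
- Japanese/non-Japanese: 153.6/136.0 = 1.129 (0.768 to 1.661).

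These only show that the ratio and SE do not move. They are not projections: F is defined on AUC∞, and 168 h is about one expected half-life.

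**Step 5: degrees of freedom.** SAS was not run, so Kenward-Roger behaviour under the SAP code is untested. A Satterthwaite calculation with a generalised inverse gives Var(SE²) = (1/3)²/617.3 = 0.00018 and df = 2 × 0.03²/0.00018 = 10, the ANOVA value.

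**The case against.** The case for leaving this alone is as follows. No hypothesis is tested, the secondary endpoints are ratios, and the ratios and SEs do not depend on the split. The model %CV is an extra descriptive line beside gCV%. The 0 to 30.7% span lists every possible split of an assumed variance and says nothing about what the software would print. A pooled %CV will differ from each cohort's gCV% even when correctly defined. One sentence stating that the components are summed would settle it. The code is labelled as a sample. The second ethnicity description is not pure duplication, because it alone names the three parameters and specifies exponentiation to a ratio with its CI.

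Much of this stands. It keeps the point minor, the span is a range of indeterminacy rather than an expected error, and the content specific to the second ethnicity paragraph must be kept. Harm to the CIs has not been shown either.

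Three things do not stand. The random participant effect is in the SAP prose as well as in the code. The sum rule that would make the %CV correct is not written. And ordinary disagreement with the cohort gCV% is bounded: for the same participants, the pooled variance is a df-weighted average of the two cohort variances, so its %CV lies between the two gCV% values. A participant-row %CV can fall below both.

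**Conclusion.** The concern holds and is minor. As specified, both models are over-parameterised, and the promised between-participant %CV has no unique value. Under an assumed total CV of 30.7% it can be anything from 0 to 30.7% at the same likelihood, and the upper end scales with whatever the true total CV is. F, the Japanese/non-Japanese ratio and their SEs are not biased.

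Non-identifiability and the missing definition follow from the design and do not depend on the assumed variance; only the size does. Kenward-Roger output from SAS remains the one untested element.

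**What to change.** - Delete both RANDOM statements in SAP 6.5 and the random participant effect from both descriptions in SAP 4.12.4.
- For Cohort 2 against Cohort 4, keep one model: the ANOVA of ln PK on cohort in protocol 9.4.2.1. Carry over the restriction to AUC∞, AUCt and Cmax, and the exponentiated ratio with its 95% CI.
- Use the same form for ln AUC∞ in Cohort 2 against Cohort 3. Residual df are 10 if all 12 are evaluable, and 9 or 8 if one or two are excluded.
- Define the model %CV as 100·sqrt(exp(MSE) - 1), the pooled form of the SAP's own gCV formula.
- As a safeguard only, state the class order or reference level so that the contrast is SC minus IV. Nothing in the documents shows that it would be inverted.

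If the mixed model is kept for programming reasons, the minimum is a sentence saying that the %CV uses the sum of the participant and residual components, with the shared intercept removed from the ethnicity code. That leaves the singular fit in place, so deletion is cleaner.

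The cost is SAP wording and a few lines of sample code, with no change to data, sample size or the reported ratios.

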## 9.4.2. Other Analyses

## 9.4.2.1. Pharmacokinetic Analysis

All PK analyses will be performed on the PK Set and will be reported by each cohort. The individual serum concentration data from participants who receive ALXN1910 with actual sampling dates and times will be used to derive the PK parameters by non-compartmental analyses methods using Phoenix WinNonlin version 6.3 or higher.

The following PK parameters will be derived:

Parameter	Definition
$C_{max}$	Maximum observed serum concentration
t max	Time to maximum observed serum concentration
AUCt	Area under the serum concentration-time curve from time 0 (dosing) to the last quantifiable concentration
$\mathrm{AUC}_{\infty}$	Area under the serum concentration-time curve from time 0 (dosing) to infinity
$t_{1/2}$	Terminal elimination half-life
$\lambda_{\rm z}$	Terminal-phase elimination rate constant
CL or CL/F	Total body clearance or apparent clearance
Vd or Vd/F	Volume of distribution or apparent volume of distribution
F	Absolute bioavailability

The F for the ALXN1910 SC cohorts will be defined by the ratio of the geometric means for the area under the serum concentration-time curve from time 0 (dosing) to infinity parameter for the ALXN1910 SC cohort over the ALXN1910 IV cohort. For the F estimates, a 95% CI for each of the ratios of the geometric means will be provided.

The PK parameters for ALXN1910 will be evaluated for Japanese and non-Japanese participants (Cohort 2 versus Cohort 4) on active treatment, using an analysis of variance statistical model with cohort as the fixed effects on the natural logarithms of the data. In addition, the Japanese versus non-Japanese cohorts will be evaluated using descriptive statistics; for each cohort, the geometric means and the associated 95% CIs of difference of PK parameters will be reported.

Dose-proportionality will be assessed and additional ALXN1910 PK parameters may be calculated if deemed appropriate with details to be provided in the SAP.

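### SAP 4.12.4 accepts dose proportionality when the 95% CI of the power-model slope excludes 0, but the proportional value is 1

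*SAP*

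**What the plan says.** Protocol 9.4.2.1 gives no criterion. It says "Dose-proportionality will be assessed and additional ALXN1910 PK parameters may be calculated if deemed appropriate" and leaves the details to the SAP.

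SAP 4.12.4 (Assessment of Dose Proportionality) supplies them. It uses Cohorts 2, 5 and 6 and three parameters: Cmax, AUCt and AUC to infinity. The model is stated as "PK parameters will be used to perform a LS linear regression analysis, using the formula ln_PK parameter =A× ln_dose + B". The response "represents the natural log transformed C_{max} and AUC parameters", and the SAP adds: "The estimate obtained for A is a measure of dose proportionality". The slope, the intercept and their 95% CIs are to be estimated. Proportionality is then accepted, which the SAP glosses as not being rejected, "if the 95% CIs of the slope does not include 0 for each PK parameter".

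The sample code in SAP 6.5 agrees with the model. It runs "PROC REG DATA = PP ALPHA=0.05 PLOTS=ALL" with "MODEL LNAVAL=LNDOS/CLB" and defines the response as "LNAVAL: natural log-transformed PK parameter". It requests confidence limits for the coefficients and contains no test against 1.

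**The concern.** The model is equivalent to exposure = e^B × dose^A. Exposure is proportional to dose when A = 1, and does not depend on dose when A = 0. A CI that excludes 0 therefore shows only that exposure changes with dose. A precisely estimated negative slope would also pass. Neither document compares A with 1 or sets a range around it.

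The sentence does not fit its own gloss either. A CI that excludes 0 rejects the hypothesis A = 0. Describing acceptance as non-rejection makes sense only if the hypothesis is A = 1 and the CI contains 1.

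Dose normalisation does not rescue the rule. The response is not dose-normalised. If it were, 0 would be the proportional slope, but the CI would then have to include 0, which is the opposite of what is written.

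At stake is the conclusion on proportionality. Followed literally, the rule can report clearly sub- or supra-proportional exposure as proportional.

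**Working it through.** **Plan's own figures.** The plan gives no error rate for this rule, so there is none to reproduce. The adverse-event probabilities in protocol 9.2 and SAP 3.2 confirm the cohort size: 1 − 0.9^6 = 46.9%, as stated for 6 active participants.

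**Inputs**
- Doses 15, 45 and 135 mg, two 3-fold steps and a 9-fold range (SAP 4.12.4; protocol 4.4).
- Active participants per cohort: 8 × 3/4 = 6, so 18 points and 16 degrees of freedom (SAP 3.1).
- Two-sided 95% CI (SAP 6.5).
- Between-participant CV: not given. Assumed 30% to 60%, with 80% and 100% as a stress check.

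**Precision of the slope**
- Sxx = 12 × (ln 3)² = 12 × 1.207 = 14.48, because the middle dose lies at the mean of log dose.
- SE(A) = √ln(1 + CV²) / √Sxx. At CV 30%: 0.294 / 3.806 = 0.077.
- CI half-width = t(0.975, 16) × SE = 2.120 × SE.

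**Meaning of the slopes over a 9-fold dose range:** 9^0.5 = 3-fold, 9^0.75 = 5.2-fold, 9^1 = 9-fold, 9^1.5 = 27-fold.

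**Results.** One-parameter figures are from the noncentral t distribution. Three-parameter figures are from 40,000 simulated trials per setting, with equal slope and CV for the three parameters and correlation between them from 0 to 0.95.

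| | CV 30% | CV 40% | CV 50% | CV 60% |
|---|---|---|---|---|
| SE of slope | 0.077 | 0.101 | 0.124 | 0.146 |
| 95% CI half-width | 0.164 | 0.215 | 0.263 | 0.309 |
| SAP rule accepts slope 0.5, one parameter | 100% | 99.6% | 96.5% | 89.6% |
| SAP rule accepts slope 0.5, all three | 100% | 99% | 90–95% | 72–86% |
| SAP rule accepts slope 1.5, all three | 100% | 100% | 100% | 100% |
| SAP rule accepts slope 0.25, one parameter | 86% | 64% | 47% | 36% |
| CI includes 1 when slope is 0.5 or 1.5, one parameter | 0.0% | 0.4% | 3.5% | 10.4% |
| CI includes 1 when slope is 0.75, one parameter | 14% | 36% | 53% | 64% |

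If the true slope is 0, the SAP rule accepts in 5% of trials. That is how a test for any dose dependence behaves.

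**Higher CV.** For slope 0.5 on one parameter, acceptance is 72% at CV 80% and 57% at CV 100%. If all three must pass, it is 37–65% and about 19–50%.

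**Comparison with the protocol's expectation.** Protocol Table 6 predicts Cmax of 1.2, 3.3 and 10.2 µg/mL at 15, 45 and 135 mg SC. The slope is ln(10.2/1.2) / ln 9 = 2.140 / 2.197 = 0.97. Predicted AUC over 168 h rises from 136.0 to 1208.8, a slope of 2.185 / 2.197 = 0.99. At CV 30% to 60% the SAP rule would usually return the same verdict for these slopes as for 0.5.

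**The case against.** The strongest defence is that little depends on the sentence. Dose proportionality is not an objective or endpoint (protocol 3), and protocol 9.1 tests no hypotheses. The regression needs Cohort 6, the last cohort, so it cannot steer escalation. The slope, its 95% CI, a figure with the CI, and box plots of dose-adjusted parameters are already planned (SAP 4.12.2 and 4.12.4), so a reader can make the comparison with 1. The non-rejection gloss also suggests a drafting slip. All of this stands and limits the importance of the point, but the written rule is still the wrong one.

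Three narrower points also stand:
- For slope 0.5, acceptance in most trials depends on the CV. It can fail at 80% or more if all three parameters must pass. The SAP wording can also be read parameter by parameter, where acceptance stays at 57% or more up to CV 100%.
- Eighteen participants is a maximum. The first withdrawal in a cohort may not be replaced (protocol 7.3), and AUC to infinity is dropped when the extrapolated share exceeds 30% or the fit is poor (SAP 4.12.2, Table 3). The effect is modest: with 5 per cohort and CV 50%, slope 0.5 is still accepted on one parameter in 92.4% of trials.
- Judging a CI against 1 without a margin is not a strong test. It flags trivial departures when the CV is low and misses moderate ones when it is high. A margin or purely descriptive reporting would be equally defensible.

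**Conclusion.** The concern holds. The acceptance rule uses the wrong reference value, and nothing elsewhere in either document corrects it. Assuming 6 active participants per cohort and a CV of 30% to 60%, the rule would call a true slope of 0.5 proportional in about 90% to 100% of trials on one parameter, and in 72% to 100% if all three must pass. A slope of 1.5 would be accepted in essentially every trial. Very shallow slopes with a high CV often fail the rule, so it does not accept everything.

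The sentence should be corrected, but the damage is confined to the proportionality conclusion. The planned estimates are sound, and the primary safety analysis and dose escalation are unaffected.

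**What to change.** Replace the acceptance sentence in SAP 4.12.4 with wording such as:

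> Dose proportionality corresponds to a slope of 1. For each PK parameter, the slope, its 95% CI and the implied exposure ratio over the 9-fold dose range will be reported and interpreted against 1. A CI that excludes 1 indicates departure from proportionality. A CI that includes 1 will be described as consistent with proportionality, not as proof of it.

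Interpret each parameter separately. Requiring all three CIs to include 1 would fail a truly proportional drug in about 7–14% of trials. The same chance of at least one flagged departure remains when the parameters are read separately, so an isolated departure should be judged by its size.

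The cost is one sentence, with no new data and no code change, since the regression already requests the 95% limits. Because the SAP is final, Section 1 requires the change to be recorded in a Statistical Method Modification Form. If the database is already locked, it belongs in the CSR and, if applicable, a SAP addendum. The small downside is that a CI including 1 is weak evidence with 18 participants, as the slope 0.75 row above shows, so the CI width must accompany the conclusion.
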